7.5.2.1 Liver Enzymes and Total Bilirubin

The following potentially clinically significant (PCS) criteria for liver tests – defined as Alkaline Phosphatase (ALP), Alanine Transaminase (ALT), total bilirubin (TBL), Aspartate Transaminase (AST) and their combination are defined. The subject's highest value during the investigational period will be used.

Parameter	Criteria
ALT	> 3xULN

	> 5xULN	
	> 10xULN	
	> 20xULN	
AST	> 3xULN	
	> 5xULN	
	> 10xULN	
	> 20xULN	
ALT or AST	> 3xULN	
Total Bilirubin	> 2xULN	
ALP	> 1.5xULN	
ALT and/or AST AND Total Bilirubin (*)	(ALT and/or AST > 3xULN) and total bilirubin > 2xULN	

(*) Combination of values measured within same sample

The PCS of liver enzymes and total Bilirubin data will be summarized and listed.

7.5.3 Vital Signs

Vital signs will not be collected for this study.

7.5.4 Electrocardiograms (ECGs)

ECG data will not be collected as stand-alone data. Any abnormal ECG results will be reported as AEs. No separate ECG results will be presented.

7.5.5 Other Safety-Related Observations

For the plasma exchange therapy with reason of Post-Transplant AMR Treatment, the number and percentage of subjects who received therapy, and the total number of sessions will be reported by treatment group.

The number and percent of subjects who undergo any antibody removal therapy or get any transfusions during the study will be reported by treatment group

7.6 Analysis of PK

Not applicable

7.7 Analysis of PD

Not applicable

7.8 Other Analyses

Not applicable

7.9 Interim Analysis

An interim analysis was conducted after 50% of control subjects had completed one year of therapy, following the procedures as described in the protocol and SAP version 1. The results of the interim analysis lead to the following decision:

1. The study would continue to enroll to completion.
2. The study duration would be such that subjects will complete at least one year of study visits.
 - a. Subjects who had not yet completed one year of study (at the time of the interim analysis) would complete the study at the 12m visit.
 - b. Subjects who had already completed the 12m visit (at the time of the interim analysis) would complete the study at their next scheduled study visit.
3. Data analysis would be performed once all subjects complete 12 months of study.

7.10 Handling of Missing Data, Outliers, Visit Windows, and Other Information

7.10.1 Missing Data

Generally, all missing efficacy endpoints (e.g. DSA, IA, pathological findings, eGFR) will not be imputed. Only for the sensitivity analyses, e.g. the sensitivity analysis of primary endpoint (section 7.4.1.2), the indetermined endpoint will be imputed as Negative.

In AE summary tables, the missing AE severity and relationship to study drug will be replaced with the highest level of severity and relationship: “Severe” and “Probable”, respectively. In AE data listing, original missing data will be displayed.

As a general principle, no imputation of missing data for other variables will be done.

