6 DISCONTINUATION

6.1 Discontinuation of Individual Subject(s)

A discontinuation is a subject who enrolled in the study and for whom study treatment is permanently discontinued prematurely for any reason.

The subject is free to withdraw from the study treatment and/or study for any reason and at any time without giving reason for doing so and without penalty or prejudice. The investigator is also free to terminate a subject's involvement in the study at any time if the subject's clinical condition warrants it.

If a subject is discontinued from the study with an ongoing AE or an unresolved laboratory result that is significantly outside of the reference range, the investigator will attempt to provide follow-up until the condition stabilizes or no longer is clinically significant. However, other than pertinent information regarding the AE (i.e., follow-up laboratory values, AE information updates, etc.), no additional clinical information will be collected following the discontinuation.

Discontinuation Criteria from Study for Individual Subjects:

- Subject develops allograft loss (as defined by subject death, retransplantation, transplant nephrectomy, or return to dialysis of ≥ 6 consecutive weeks duration);
- Subject develops unacceptable toxicity or is withdrawn at the discretion of the patient's supervising physician;
- Subject is lost to follow-up despite reasonable efforts by the investigator to locate the subject;
- Subject withdraws consent for further treatment or expires during the course of the study;
- Subject begins taking any prohibited medications (see Section 5.1.5);
- Subject undergoes a second organ transplant;
- Conversion to a non-tacrolimus-based maintenance regimen in either study arm if required to manage toxicities;
- Removal from an MMF-containing immunosuppressive regimen (or its equivalent);
- Failure to achieve a tacrolimus whole blood concentration ≥ 6 ng/mL for 4 consecutive weeks during the first 6 weeks following transplantation;
- Permanent withdrawal of tacrolimus;
- Interruption or prolonged significant reduction of tacrolimus (as an example, a 50% reduction or dose at a level of less than 3.5ng/mL) for periods exceeding 4 weeks;

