These threshold endpoints will be calculated for months 1, 3, 6, 9, and 12 using the Modification of Diet in Renal Disease (four variable-MDRD) criteria. Assessments are positive or negative.

- Five-point decline in eGFR

The decline in eGFR will be calculated with respect to the eGFR value at Day 30 visit.

- Traditional transplantation composite endpoint

Incidence will be assessed at month 12 for the following:

- Graft loss (defined as retransplantation, transplant nephrectomy, or a return to dialysis for at least a six week duration, or subject death)
- Death
- BPAR – positivity will be determined by local biopsy, central pathology, or reported adverse events.
- Composite occurrence of either graft loss, death, BPAR, and loss-to-follow-up

- Histopathology grading within 1 year

Central histopathology grading over 1 year will be diagnosed according to the BANFF diagnostic categories and subcategories that include the following:

- Normal
- Antibody mediated changes
 - C4d deposition without morphologic evidence of active rejection
 - Acute ABMR (grades: I, II, and III)
 - Chronic active ABMR
 - ABMR: either Acute ABMR or Chronic Active ABMR
- Borderline changes
- TCMR
 - Acute TCMR (grades: IA, IB, IIA, IIB, and III)
 - Chronic active TCMR
- IFTA (grades: I, II, and III)
- Other: all categorical findings will be summarized.
- In addition to the categories above, specimens will be given individual scores for the following: glomerulitis (g), tubulitis (t), intimal arteritis (v), mononuclear cell interstitial inflammation (i), early allograft Glomerulopathy (cg), tubular atrophy (ct), interstitial fibrosis (ci), vascular fibrous intimal thickening (cv), arteriolar hyaline thickening (ah), peritubular capillaries (ptc) and mesangial matrix (mm).

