7.4.2 Analysis of Secondary Endpoints

Risk factor analysis will be conducted in two parts. First, is to identify risk factors for outcomes based on factors measured at time of transplantation (baseline) including the pre-defined stratification factors. Last, is to identify risk factors for outcomes based on factors that are measured post-randomization and therefore, are subject to change e.g., average daily dose of MPA treatment or cumulative dose of corticosteroids. All models will include randomized treatment, irrespective of statistical significance. Models to assess risk factors for binary or categorical variables will be done using logistic regression. Odds ratio and 95% CI will be used as measures of strength of association and precision, respectively.

Risk factor analyses will be conducted for eight binary variables: IFTA, IFTA and Inflammation, BPAR, the four-part traditional composite endpoint, early MMF interruption/discontinuation, and eGFR status based on three thresholds 30, 40, and 50. The biopsy data are based on the central pathology results over the course of one year plus 2 months window. eGFR status variables are based on the assessment at Day 365 visit.

Each risk factor analysis model will include treatment group and a main factor: either De novo DSA, IA, or the composite of De novo DSA and IA. Following additional covariates will be considered for the two types of models, and a multicollinearity assessment will be proceeded for the final variable selection:

Risk factors measured at time of transplantation include:

- Cold ischemic time
- Warm ischemic time

- KDPI% \leq 50% (yes/no)
- KDPI% $>$ 50% (yes/no)
- HLA Class II mismatch (yes/no)
- Donor status (living/deceased)
- Donation after circulatory death (yes/no)
- Donor Age
- Donor-Recipient sex mismatch (match/mismatch)
- Donor-Recipient race mismatch (match/mismatch)
- Preservation by cold storage (yes/no)

Post randomization risk factors include:

- Cumulative Dose of Corticosteroids
- Average daily dose of MPA
- Mean dose level of tacrolimus
- Mean tacrolimus trough level
- Number of excursions below 80% or above 120% of the average tacrolimus trough level
- IPV estimated by CV%
- Post-transplant BK virus infection

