Following secondary endpoints will be summarized with frequencies and percentages by treatment group. The incidence of events will be analyzed for treatment group differences. Analysis of treatment group differences will be implemented from logistic regression model with the same covariates of primary efficacy analysis.

1. De novo DSA formation
2. IA
3. C1q-binding DSA
4. DSA IgG₃ isotype
5. Persistence of DSA
6. Persistence of IA
7. TG (cg $>$ 0)
8. Microcirculatory Inflammation (g+ptc $>$ 2)

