9. IFTA
10. IFTA and Inflammation (IFTA and ci $>$ 0)
11. Acute and chronic forms of ABMR
12. eGFR at various thresholds (less than 30, 40, 50 mL/min/1.73 m² at one year; and a five-point decline from Day 30 to Day 365)
13. Graft loss
14. Mortality

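### Patients who lose the graft before about Day 304 drop out of the one-year eGFR <30/40/50 analyses, because the SAP has no rule for scoring a lost graft

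*SAP*

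**What the plan says.** - **Endpoint.** SAP 7.4.2 lists eGFR "less than 30, 40, 50 mL/min/1.73 m² at one year" among the secondary endpoints compared between arms, using a "logistic regression model with the same covariates of primary efficacy analysis". SAP 6.1.2 makes each threshold binary: "Assessments are positive or negative".
- **Risk-factor models.** Three of the eight outcomes in SAP 7.4.2 are the eGFR thresholds, and "eGFR status variables are based on the assessment at Day 365 visit". The main factor in each model is de novo DSA, IA or their composite.
- **Missing values.** SAP 7.10.1: "Generally, all missing efficacy endpoints (e.g. DSA, IA, pathological findings, eGFR) will not be imputed".
- **Substitution.** SAP 7.10.3 replaces a missing scheduled Day 365 value with the nearest unscheduled value within 61 days either side.
- **Discontinuation.** Among the criteria in protocol 6.1 is: "Subject develops allograft loss (as defined by subject death, retransplantation, transplant nephrectomy, or return to dialysis of ≥ 6 consecutive weeks duration". Apart from information on ongoing adverse events, "no additional clinical information will be collected following the discontinuation".
- **Graft loss elsewhere.** SAP 6.1.2 analyses graft loss, with death included in its definition, as its own endpoint and within the four-part composite. SAP 7.10.3 cuts it off at Day 365.
- **Minimum event rate.** SAP 7.1 fits no regression for an outcome with an event rate below 10%.

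**The concern.** A patient who has returned to dialysis, been retransplanted or had the graft removed has function in that graft below all three thresholds. Under the rules above, the same event usually leaves no Day 365 eGFR. The patient then leaves both numerator and denominator of an endpoint meant to count poor kidney function.

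Missingness of this kind is related to the outcome. It lowers the reported below-threshold rate in each arm where it occurs. If graft loss differs between arms, or between patients with and without DSA or IA, the comparisons among the remaining patients can be biased. The five-point decline from Day 30 to Day 365 has the same gap.

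**Working it through.** The documents give no expected graft-loss rate and no expected eGFR threshold rate, so there is no plan figure to reproduce on this point. The sample-size calculation concerns the primary composite and is not used here.

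**Step 1. Trace a graft loss other than death through the rules.** The substitution window runs from 365 − 61 = Day 304 to 365 + 61 = Day 426. Dialysis counts as graft loss only after six weeks, so dialysis begun after about 365 − 42 = Day 323 has not met the definition by Day 365.

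| Timing | Day 365 eGFR under the plan |
|---|---|
| Loss before about Day 304 | No eligible value; patient excluded |
| Loss from about Day 304 to Day 365 | Missing, or scored on a value in the window that may predate the loss |
| Dialysis begun after about Day 323 | Not yet a discontinuation at Day 365; a value may exist |

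No section scores a lost graft as below threshold. The SAP also does not say whether a creatinine taken on dialysis is eligible.

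**Step 2. Effect on the rate.** Let *g* be the share with graft loss other than death and no eligible eGFR, and *q* the share below threshold among the others, all taken as measured. Both are assumptions. The SAP reports *q*. Counting graft loss gives *g* + (1 − *g*)*q*, a difference of *g*(1 − *q*).

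| *q* | *g* | SAP reports | Graft loss counted |
|---|---|---|---|
| 10% | 3% | 10% | 0.03 + 0.97 × 0.10 = 12.7% |
| 8% | 3% | 8% | 0.03 + 0.97 × 0.08 = 10.8% |
| 4% | 2% | 4% | 0.02 + 0.98 × 0.04 = 5.9% |
| 4% | 3% | 4% | 0.03 + 0.97 × 0.04 = 6.9% |
| 4% | 5% | 4% | 0.05 + 0.95 × 0.04 = 8.8% |

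Over *g* = 1% to 5% and *q* = 3% to 20%, the understatement runs from 0.01 × 0.80 = 0.8 points to 0.05 × 0.97 = 4.85 points.

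**Step 3. The 10% rule in SAP 7.1.**
- At *q* = 4%, every row stays below 10% with or without graft loss. No model is fitted and only the descriptive rate changes.
- At *q* = 8% and *g* = 3%, the rate crosses 10%, so the choice decides whether a model is fitted at all.
- At *q* = 10%, the rate reaches 10% either way.

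**Step 4. Effect on the arm comparison.** Take *q* = 10% in both arms and graft loss of 5% against 2%. The observed-case odds ratio is 1.00. Counting graft loss gives 0.05 + 0.95 × 0.10 = 14.5% against 0.02 + 0.98 × 0.10 = 11.8%. The odds ratio is then (0.118/0.882)/(0.145/0.855) = 0.79. Which arm has more losses is arbitrary here; swapping them inverts the ratio.

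**The case against.** **Function among surviving grafts is a legitimate question.** Graft loss is reported separately and in the four-part composite, and thresholds are also calculated at months 1, 3, 6 and 9. A reader can see an arm with more losses and any decline recorded before them. That is true, but it does not return these patients to the one-year comparison or the risk-factor models, and the SAP does not say that it intends a functioning-graft analysis.

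**Not every graft loss is excluded.** A reader might infer from SAP 7.10.1 alone that every patient who loses the graft is dropped. That sentence is qualified as a general rule, and the Day 304 to 426 substitution can keep a later loss in. The firm statement is limited to losses before about Day 304.

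**Graft loss as defined includes death.** Death with a functioning graft is not evidence of eGFR below 30, so it cannot be counted in *g*.

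**Direction of bias.** A reader might infer that the DSA and IA associations are attenuated. Protocol 1.1 calls DSA a strong predictor of graft failure, which makes this plausible. However, SAP 7.4.1.1 takes de novo DSA as negative for patients who leave between Day 0 and Day 30 without results. Counting such early losses would add DSA-negative events and could itself weaken the association. The documents do not settle the direction.

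**Importance.** These are secondary endpoints in a trial described as exploratory, with no multiplicity adjustment. This limits the weight of the point but does not answer it.

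**Conclusion.** The point holds in this form: graft losses other than death before about Day 304 leave the one-year threshold comparisons and the three eGFR risk-factor outcomes, and later losses may be missing or scored on a pre-loss value. This follows from protocol 6.1 and SAP 7.4.2, 7.10.1 and 7.10.3 read together; no single sentence states it and none overrides it.

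The size rests on assumed rates. The understatement is 2.7 points at *q* = 10% and *g* = 3%, and 0.8 to 4.85 points over the range shown. At *q* = 4% the relative understatement looks large, 1 − 4/5.92 = 32% to 1 − 4/8.8 = 55%. A reader might take that as distortion of the modelled results, but SAP 7.1 would allow no model at those rates, so it concerns the descriptive rate only. The arm comparison and the DSA/IA associations can be biased, in an unestablished direction. The primary endpoint is not affected. The change should be made, but the primary analysis does not depend on it.

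**What to change.** In SAP 6.1.2 and 7.10:

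1. Count retransplantation, transplant nephrectomy or return to dialysis that meets the graft-loss definition by the Day 365 cut point as eGFR below 30, 40 and 50. This status takes precedence over any substituted eGFR value.
2. Count such a loss as a five-point decline only when it follows an available Day 30 eGFR, since earlier losses have no baseline.
3. Leave death with a functioning graft as missing.
4. Show the functioning-graft (observed) analysis beside it, and report the numbers excluded by arm and reason.

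The cost is one derivation rule. No new data are needed, because graft-loss status to Day 365 is already analysed. The downside is that the endpoint becomes graft loss or eGFR below threshold, which is why the observed analysis must sit beside it. Dialysis begun too late to meet the six-week definition by Day 365 stays under the observed-value rule.

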7.10.2 Outliers

Unless otherwise specified, all values will be included in the analyses.

7.10.3 Visit Windows

Visit windows are defined in Section 2 (Flow Chart and Visit Schedule). For all data collected by visit, the assessments will be presented per the scheduled visits. For data collected by date (e.g. start/stop dates) or collected at unscheduled visits, following rules are applied:

- Study treatment and Tacrolimus trough level – All data from Day 30 to Day 365 will be used in calculation. In the calculation of IPVs, only data after Day 42 (i.e. 6 weeks) will be used.
- Central pathology – All data from Day 0 to Day 426 (Month 14 = 365 + 61) will be included in the calculation of endpoints related to central pathology, e.g. IFTA, Acute Rejection, etc.

- Serum creatinine and eGFR – If the scheduled Day 30 assessment is missing, it will be imputed using the unscheduled assessment within Day 30 +/- 14 window that is closest to Day 30; If the scheduled Day 365 assessment is missing, it will be imputed using the unscheduled assessment within Day 365 +/- 61 window that is closest to Day 365.
- All other primary and secondary endpoints will use the data up to Day 386.
- Death, graft loss, immunosuppressant total dose, and other safety endpoints - Day 365 will be used as cut point for the one-year analysis.

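### The one-year four-part composite mixes cut-offs: Day 365 for death and graft loss, Day 426 for centrally read rejection, and Day 386 by default for local-biopsy rejection

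*SAP*

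**What the plan says.** SAP 6.1.2 places the traditional transplant endpoints at month 12. The composite is "Composite occurrence of either graft loss, death, BPAR, and loss-to-follow-up". BPAR has three possible sources: "positivity will be determined by local biopsy, central pathology, or reported adverse events".

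SAP 7.10.3 then sets the data windows:

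- Central pathology: "All data from Day 0 to Day 426 (Month 14 = 365 + 61) will be included", for "endpoints related to central pathology, e.g. IFTA, Acute Rejection, etc".
- Default: "All other primary and secondary endpoints will use the data up to Day 386".
- Clinical and safety events: "Death, graft loss, immunosuppressant total dose, and other safety endpoints - Day 365 will be used as cut point for the one-year analysis".

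SAP 7.4.2 repeats the one-year-plus-two-months biopsy window for risk-factor models whose outcomes include BPAR and the composite. It also compares both between arms by logistic regression. No section gives the composite a cut-off of its own.

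SAP 7.9 records the interim decision. Patients who had not yet reached one year "would complete the study at the 12m visit"; those already past that visit stayed until their next scheduled one.

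**The concern.** A composite rate at one year needs the same time at risk for each component. As written, a patient who dies or loses the graft on Day 370 has no event from that death or loss, while a patient with rejection on a centrally read biopsy on Day 420 can have one. The resulting proportion is neither a Day 365, a Day 386 nor a Day 426 rate.

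The later part of the rejection window is also unevenly observed. Follow-up over Days 387 to 426 is assured only for patients already past the 12-month visit at the interim. The protocol (7.4.2) planned Cox models with censoring for BPAR and the composite, which would have handled unequal follow-up. The SAP's revision history (item 5) drops the time-to-first-occurrence analyses, and a binary logistic model makes no such allowance.

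**Working it through.** **1. Reproduce the SAP's days.** Month 14: 365 + 61 = 426, as stated. The default of 386 is 365 + 21, the end of the ±21-day window in the visit schedule. That window opens at 365 − 21 = Day 344.

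**2. Set the cut-offs side by side.**

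| Component | Source | Cut-off under 7.10.3 |
|---|---|---|
| Death, graft loss | clinical record | Day 365 |
| BPAR | central pathology | Day 426 |
| BPAR | local biopsy | Day 386 (default rule) |
| BPAR | adverse event | unclear: Day 386 as efficacy, Day 365 as safety |
| Loss to follow-up | not defined in the SAP | none stated |

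The largest gap is 426 − 365 = 61 days, and 61/365 = 16.7%. From Day 365 to Day 386 it is 21 days, and 21/365 = 5.8%.

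**3. Which late biopsies can count.** Under SAP 3.2 (protocol 5.3.7), one biopsy per patient is sent for central grading: the one nearest the 12-month visit, no later than 14 months, and only in patients with at least one biopsy in the first year. With the visit on Day 365, a Day 420 biopsy lies 55 days away. It is selected only if the first-year biopsy was before 365 − 55 = Day 310.

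**4. Who is followed that long.** Patients not yet at 12 months at the interim exit between Day 344 and Day 386, which is 426 − 386 = 40 to 426 − 344 = 82 days before Day 426. Patients already past that visit stay until a visit at nominal Day 455 or later. The earliest date in that window is 455 − 21 = Day 434, so they cover Day 426.

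The number in each group is not documented. With the trigger at 50% of 275 planned controls, 1 − 137.5/275 = 50% had not completed one year. With the 110 controls used in protocol Appendix 12.4, the figure is 1 − 110/275 = 60%. Both shares include patients who had already dropped out.

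**5. Size for BPAR.** The documents give no BPAR rate, so a one-year risk p is assumed, with constant hazard. The risk by day d is 1 − (1 − p)^(d/365).

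| Assumed p (Day 365) | Day 386 | Day 426 | Added, Day 365 to 426 |
|---|---|---|---|
| 5% | 5.3% | 5.8% | 0.8 points |
| 10% | 10.5% | 11.6% | 1.6 points |
| 15% | 15.8% | 17.3% | 2.3 points |
| 20% | 21.0% | 22.9% | 2.9 points |

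These figures assume that everyone is observed to Day 426 and every rejection is centrally read, so they are upper bounds under the constant-hazard assumption. If 40% or 50% are observed to Day 426 and the rest to Day 386, an assumed 10% becomes 10.95% or 11.06%.

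**6. A side effect.** SAP 7.1 runs no regression for outcomes with an event rate below 10%. For an assumed p of 9%, the formula gives 1 − 0.91^(386/365) = 9.5% by Day 386 and 1 − 0.91^(426/365) = 10.4% by Day 426. Near that threshold, the window could decide whether the model is fitted.

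**The case against.** The strongest reply is that the two-month allowance is deliberate. SAP 3.2, 6.1.2 and 7.4.2 all use it, because a biopsy intended for month 12 may be taken late. Acute rejection in 7.10.3 could also mean the central Banff categories and not BPAR, which is the SAP's name for the composite's component. SAP 6.1 bases efficacy on data from the one-year period, and both arms share the same windows and exit rule.

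Part of this stands. The allowance is sensible for lesions read from the biopsy, and the cut-offs for local-biopsy and adverse-event BPAR are inferred, not stated. But 6.1.2 attaches the two extra months to transplant glomerulopathy (TG), microcirculatory inflammation, and interstitial fibrosis/tubular atrophy (IFTA) with inflammation, and not to BPAR or the composite. The window sentence in 7.4.2 does cover models with BPAR and the composite as outcomes. If the narrower reading is intended, the SAP does not say so.

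A reader might go further in three ways that the documents do not support:

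- **Every centrally read rejection on Days 366 to 426 is added.** The one-biopsy rule and the first-year-biopsy condition prevent this.
- **Only early enrolees add events, or later ones have no data after month 12.** Later enrolees can contribute up to Day 386, and new serious adverse events are reported for 7 days after the last visit. Whether biopsies after exit are collected is not stated.
- **The composite ranks rejection above death.** It is an unranked yes/no outcome.

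**Conclusion.** The inconsistency holds: following the SAP as written, the components of one composite stop at Day 365, Day 386 and Day 426. The discrepancy is up to 61 days. Its effect on BPAR is at most about 0.8 to 2.9 percentage points for assumed one-year risks of 5 to 20% under a constant hazard, and less if the hazard falls over time or late biopsies are incompletely captured. The actual number of events affected cannot be derived from the documents.

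It would be tempting to infer a biased treatment comparison. That is not shown, because windows and exit rule are identical in both randomised arms. The primary DSA/IA endpoint is not touched. The damage is to the interpretation of the one-year BPAR and composite rates, in the arm comparisons and the risk-factor models, and to comparability between early and late enrolees. It should be corrected, as a secondary-endpoint matter.

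**What to change.** In SAP 6.1.2, 7.4.2 and 7.10.3, apply one cut-off to BPAR from any source and to all four components of the composite. Day 386 is the natural choice: it is the SAP's own default and the end of the 12-month visit window. A strict Day 365 cut would discard rejection on an on-schedule biopsy taken on Days 366 to 386 while other lesions from the same biopsy still counted.

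- Date BPAR by biopsy date, or by adverse-event onset if that is the only source.
- Judge loss to follow-up at the 12-month visit, and define it in the SAP. At present only protocol 7.4.2 does.
- Keep Day 426 for the stand-alone central histology endpoints (TG, microcirculatory inflammation, IFTA, Banff scores).
- Report central rejections on Days 387 to 426 separately, so that no information is lost.

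The cost is text in three sections and slightly fewer BPAR events; no new data are needed. The composite would count deaths and graft losses to Day 386 while their stand-alone summaries stop at Day 365, unless those are aligned too. A patient seen at the start of the visit window would still fall short of the cut-off, but by at most 386 − 344 = 42 days instead of 82.
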